### **Sample Size**

Sample size will be between 420 and 1000 patients. Sample size was calculated after a pre-trial evaluation of HAI. We retrospectively measured the pre-trial incidence of HAI at ICU and PC-ICU (patients admitted to ICU and PC-ICU between January, 1st and January, 31st 2015). Twenty patients out of 66 suffered from at least 1 HAI (incidence 30.3%).

By adopting an alpha error tolerance (false-positive risk) equal to 0.05, beta error tolerance (false-negative risk) equal to 0.1, power equal to 0.9, a potential reduction of HAI incidence by 10% and a percentage between 5% and 8% of potential dropouts, we calculated that a sample size of at least 410-420 patients would be required to provide sufficient power to detect significant differences. According to the Italian Law, patients with altered mentation at the admission could be directly enrolled by the physician after a clinical evaluation. At the recovery of consciousness, the patient will receive the specific paper to provide his consent or not.

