### **Data analysis**

Data will be analysed with a statistical software. Distribution of variables will be assessed by Kologorov-Smirnov deviation. Normal variables will be represented as mean +/- standard deviation, continuous non Gaussian variables will be represented as median and interquartile range, categorical variables will be represented as frequency and percentage. Comparison between groups will be performed with two-tailed t-test, Mann-Whitney test or chi-square test with Yate's correction, depending on variable distribution. Data analysis will be made by physicians blinded to the study arm.

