### **Data collection.**

We will enrol 420 to 1000 patients in up to one year. Randomisation will be done by a specific software; it will be a simple 1:1 randomisation at patient-level. To evaluate infections we will use data from the routine clinical practice; patients in the two arms will be evaluated in the standard way and without differences between the two arms.

Data will be collected with an ad hoc clinical report form (CRF); data about sex, age, demographic characteristics, comorbidities – evaluated by Charlson comorbidity index – and infections will be collected in the same above mentioned CRF.

These data will be collected and analysed by physicians blinded to the randomisation.

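### Power of 0.9 is claimed for 410-420 patients, but 420 in total gives about 58-62% for a 10-point reduction; 90% needs about 870-900 enrolled

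*Combined protocol and SAP*

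**What the plan says.** All the inputs are in the Sample Size section. The baseline comes from one month of admissions: "Twenty patients out of 66 suffered from at least 1 HAI (incidence 30.3"%). The error rates and effect are "alpha error tolerance (false-positive risk) equal to 0.05" and "beta error tolerance (false-negative risk) equal to 0.1, power equal to 0.9, a potential reduction of HAI incidence by 10"%, with 5% to 8% dropout. The conclusion is that "we calculated that a sample size of at least 410-420 patients would be required to provide sufficient power to detect significant differences".

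The same section opens with "Sample size will be between 420 and 1000 patients". The Data collection section repeats this as enrolment for the whole trial, "We will enrol 420 to 1000 patients in up to one year", and on allocation says "it will be a simple 1:1 randomisation at patient-level".

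For categorical variables, the Data analysis section lists the "chi-square test with Yate's correction, depending on variable distribution". No section labels 410-420 as a number per arm, and none says whether the 10% is absolute or relative.

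**The concern.** Detecting a fall from about 30% to about 20% with 90% power ordinarily takes close to 400 patients in each arm. A minimum of 420 for both arms together is about half of what that implies. The stated 410-420 looks like a per-arm result used as a trial total.

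This matters because the protocol permits enrolment to end at 420 and attaches a 10% false-negative risk to that number. If the real risk is about four times as large, a null result could be read as good evidence against a 10-point benefit when the trial had little better than an even chance of finding one. The Introduction says that earlier studies of this strategy disagree, so such a misreading would carry weight.

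**Working it through.** **Inputs.** From Sample Size: p1 = 20/66 = 0.3030, alpha 0.05, power 0.90, dropout 5-8%. From Data collection: 1:1 allocation and a minimum of 420 in total. From Data analysis: chi-square test with Yates' correction. Two assumptions are mine: the test is two-sided, and the 10% is absolute, so p2 = 0.2030 and d = 0.10. The relative reading is taken separately below.

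**Required size per arm.** With z(0.975) = 1.960, z(0.90) = 1.282, p1q1 + p2q2 = 0.3730 and 2·p̄·q̄ = 0.3780:

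- Unpooled: n = (1.960 + 1.282)² × 0.3730 / 0.10² = 391.9.
- Pooled: n = (1.960·√0.3780 + 1.282·√0.3730)² / 0.10² = 395.1.
- Continuity-corrected: n = (395.1/4) × [1 + √(1 + 4/(395.1 × 0.10))]² = 414.9.

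Exact binomial enumeration agrees: the Yates-corrected test first reaches 90% power at 414 per arm.

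**Trying to reproduce 410-420.** As a per-arm number it comes out closely: 391.9/0.95 = 413 and 391.9/0.92 = 426. The continuity-corrected figure is 415 before dropout. As a trial total it does not come out. Before dropout, the unpooled and pooled totals are:

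| Setting | Total needed |
|---|---|
| Two-sided, 90% power | 784-790 |
| One-sided, 90% power | 639-644 |
| Two-sided, 80% power | 586-591 |
| One-sided, 80% power | 461-465 |

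**Enrolment needed for 90% power, with dropout.**

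- With Yates' correction: 829.7/0.95 = 873 to 829.7/0.92 = 902.
- Without it: 783.9/0.95 = 825 to 790.2/0.92 = 859.

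**Power actually delivered (exact enumeration, 30.3% v 20.3%).**

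| Enrolled | Dropout | Per arm | Yates | Uncorrected |
|---|---|---|---|---|
| 420 | 0% | 210 | 61.6% | 65.8% |
| 420 | 5% | 200 | 59.3% | 63.6% |
| 420 | 8% | 193 | 57.7% | 62.0% |
| 777 | 8% | 357 | 85.2% | 87.0% |
| 792 | 5% | 376 | 86.9% | 88.7% |
| 1000 | 8% | 460 | 92.9% | 93.9% |
| 1000 | 0% | 500 | 94.8% | 95.5% |

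The 777 and 792 rows are a full year at the January rate: 66/31 × 365 = 777 and 66 × 12 = 792, before exclusions and refusals.

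**Detectable difference at 420 (Yates, 90% power).** 13.7 points with no dropout, 14.1 with 5% and 14.3 with 8%.

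**Uncertain baseline.** The exact 95% interval for 20/66 is 19.6% to 42.9%. For a 10-point drop, Yates power at 420 is 79.1% (no dropout) to 75.1% (8%) at a control rate of 20%, and 52.2% to 49.0% at 43%. Even at 19.6% with no dropout it is only 80.0%.

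**Relative reading.** If p2 = 0.9 × p1 = 27.3%, power at 420 is 8.2-8.6% with Yates and 10.1-10.5% without. The requirement is about 4,690 per arm.

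**The case against.** The strongest objection is that 420 is only a floor. The Study design section says that all admitted patients will be enrolled, and the ceiling is 1000. A full year at the January rate would give about 85-87% power with the Yates test, and 1000 patients about 93-95%. On that view the severe loss is a worst case. This limits the practical damage but does not rescue the statement: the protocol ties power 0.9 to 410-420, permits a stop at 420, and gives no rule for choosing a size within the range.

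Three further points are fair:

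- The 58-62% and 870-900 figures depend on the absolute reading, which only the sponsor can confirm. The other reading makes the shortfall far larger.
- The 62% end of the range assumes no dropout. On the protocol's own 5-8% the Yates figure is 57.7-59.3%.
- The Data analysis section lists tests by type of variable and does not name a primary one. Yates' chi-square is the one listed for a proportion, and dropping the correction raises power at 420 only to 62-66%.

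The Study design section also says that the arms will be compared on sepsis. The documents give no baseline rate for that outcome, so these figures apply to HAI incidence only.

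**Conclusion.** The concern holds. On the protocol's own inputs, 420 patients in total give about 58-62% power (0-8% dropout, Yates-corrected, two-sided alpha 0.05) for a 10-point reduction in HAI incidence. The stated 90% needs about 415 evaluable per arm, or about 870-900 enrolled. The false-negative risk at the permitted minimum is about 38-42% against a stated 10%.

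The direction of the error does not depend on the Yates correction, two-sidedness, the absolute reading or the exact baseline: none of the alternatives tried brings 420 in total to 90%. That a per-arm number was left undoubled is a plausible inference from the match in size, but the documents show no formula. If 410-420 was meant per arm, the 420 minimum in Sample Size and Data collection is wrong instead.

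**What to change.** The sponsor should first confirm whether the 10% is absolute or relative. If absolute, replace the power statement in Sample Size with:

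> A total of 420 patients (210 per arm) gives about 58-62% power (0-8% dropout, chi-square test with Yates' correction, two-sided alpha 0.05) for an absolute reduction of 10 percentage points in HAI incidence, from 30.3% to 20.3%. The absolute reduction detectable with 90% power is about 14 percentage points. Power of 90% for 30.3% versus 20.3% needs about 415 evaluable patients per arm, about 870-900 enrolled in total with 5-8% dropout.

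If relative, say so and restate the power on that basis. In both Sample Size and Data collection, label 420 to 1000 as the total for both arms.

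This costs protocol wording only, though the stated power becomes less favourable and the minimum still falls short of the 90% target. To keep that target, raise the lower limit to about 870-900, which fits under the 1000 ceiling. That is more than wording: at 66 admissions a month it takes 873/66 = 13.2 to 902/66 = 13.7 months even if every admission is enrolled, so the one-year limit may also have to change.

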### **Data analysis**

Data will be analysed with a statistical software. Distribution of variables will be assessed by Kologorov-Smirnov deviation. Normal variables will be represented as mean +/- standard deviation, continuous non Gaussian variables will be represented as median and interquartile range, categorical variables will be represented as frequency and percentage. Comparison between groups will be performed with two-tailed t-test, Mann-Whitney test or chi-square test with Yate's correction, depending on variable distribution. Data analysis will be made by physicians blinded to the study arm.

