## **Definitions and methods:**

Demographic characteristics and clinical data of patients will be collected using a case report form that was elaborated specifically for this study (attachment 1) .

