## **Study design**

Prospective single-blinded randomized case-control study.

Study population: all patients admitted to the Intensive Care Unit (ICU) or to the Post-Cardiosurgical Intensive Care Unit (PC-ICU) of the University Hospital of Perugia will be enrolled.

These patients will be randomized in two arms using a specific software. Patients in the first arm (control arm) will undergo the usual hygiene procedures with standard soap; in the second arm (treatment arm) patients will be bathed with 4% CHG-containing soap (Neoxidina mani 4%), at least 30 ml according to the manufacturer indications (see the attached data sheet). In particular the whole body surface - except for the face - will be i) humidified

[figure not shown]
with water impregnated washcloths, ii) bathed with 4% CHG-impregnated washcloths (at least 30 ml) and, after at least 30 seconds, iii) rinsed with water-impregnated washcloths.

This product is already in use in our hospital to prepare patients before a surgical intervention. We will evaluate and compare the global incidence of sepsis in the two arms and, secondary, incidence of VAP, BSI, CABSI, UTI and CAUTI.

In addition to this, we will collect demographic data of each patients and data about comorbidities, cause of admission and infections occurred during the hospital stay.

This study is single-blind. Physicians that have to collect data, to diagnose infections and to analyse data won't be directly involved in washing procedures and they are not member of the medical staff of ICU and/or TIPOC. Moreover, only nurses that will wash patients by their own hands will know the arm in which the patient is. Both the usual soap and the Neoxidina mani 4% (with chlorhexidine gluconate 4%) have no colour nor other item than can favour their identification.

*Figure 1: Study design*

*Patients enrolment.*

Inclusion criteria: all patients aged  $\geq 18$  years old admitted to ICU or TIPOC.

Exclusion criteria:

- Age  $< 18$  years old;
- patients with burns;
- patients with known allergy to chlorhexidine and/or one of the components of Neoxidina mani 4%;
- patients with toxic epidermal necrolysis o Stevens-Johnson syndrome.
- pregnancy

Data will be collected on specific paper form and, then, analyzed using computerized methods (section "Criteria and data collection methods").

*Relative risk of the procedure and risk/benefit evaluation.*

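### The arms are to be compared by unadjusted tests that ignore unit, age and Charlson index; prespecified adjustment costs almost nothing and may gain power, by an amount the documents cannot fix

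*Combined protocol and SAP*

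**What the plan says.** The Data analysis section is the whole analysis plan. On the comparison of arms it states: "Comparison between groups will be performed with two-tailed t-test, Mann-Whitney test or chi-square test with Yate's correction, depending on variable distribution". It names no regression model, stratified test or covariate. Categorical variables will be summarised as frequencies and percentages, but no between-arm effect estimate or confidence interval is planned, adjusted or otherwise.

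On allocation, the Data collection section says "it will be a simple 1:1 randomisation at patient-level", so unit is not balanced by design. The Study design section enrols from a general ICU and a post-cardiosurgical ICU together.

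The Data collection section lists "data about sex, age, demographic characteristics, comorbidities", the last of these "evaluated by Charlson comorbidity index". Unit is not named in that list, but it follows from the admission. The case report form itself is an attachment that is not available here.

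The only event rate in the documents is the pilot figure in the Sample Size section: 20 of 66 patients with at least one HAI, pooled over both units.

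**The concern.** A general ICU and a post-cardiosurgical ICU may well carry different infection risks, and age and comorbidity may predict infection too. If so, an unstratified test leaves that variation in the error term, and a chance imbalance between arms passes straight into the estimated difference. Adjustment for variables fixed before randomisation removes both, and the trial will already hold the data.

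Prespecification also matters in its own right. Covariates chosen after the data have been seen invite selective reporting.

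The stake is power and precision. Under simple patient-level randomisation the crude test of a per-patient outcome controls its type I error, so validity is not in question.

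**Working it through.** **Inputs from the documents.** Control risk 20/66 = 30.3%; reduction 10%; "alpha error tolerance (false-positive risk) equal to 0.05"; power 0.90; dropout 5% to 8% (all Sample Size). Enrolment 420 to 1000 (Data collection).

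**Assumptions.** The 10% is read as 10 percentage points, so 30.3% against 20.3%, a risk ratio of 0.67 in both units. Tests are two-sided, 420 means the trial total, and nobody drops out. Unit-specific risks and covariate strengths are not in the documents, so ranges are used.

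**The plan's own sample size.** The pooled risk is 0.253.

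n per arm = [1.96·√(2·0.253·0.747) + 1.2816·√(0.303·0.697 + 0.203·0.797)]² / 0.10² = (1.205 + 0.783)² / 0.01 ≈ 396, or 792 in total.

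Dividing 396 by 0.95 and 0.92 gives 417 and 431 per arm. The stated 410-420 is therefore close to a per-arm figure. It is not reproduced as the total for which it is used.

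**Power of the crude test, 210 per arm.**
- Null standard error: √(2·0.253·0.747/210) = 0.0424. Alternative standard error: √(0.373/210) = 0.0421.
- Pearson: Φ[(0.10 − 1.96·0.0424)/0.0421] = Φ(0.40) = 65.5%.
- Yates, which subtracts 1/210 = 0.0048 from the difference: Φ(0.29) = 61.3%.

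**Stratifying by unit.** The Cochran-Mantel-Haenszel (CMH) statistic is [Σ(aₖ − Eₖ)]² / ΣVₖ, summed over the two units. Here aₖ is the number of treated patients with an event, and Eₖ and Vₖ are its hypergeometric mean and variance. The simulation used simple 1:1 randomisation, 400,000 trials per row, N = 420 and equal-sized units:

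| Control risk in the two units | Pearson | Yates | CMH | CMH − Pearson (points) | Equivalent extra patients |
|---|---|---|---|---|---|
| 30.3% / 30.3% | 0.657 | 0.615 | 0.655 | −0.2 | about 0% |
| 35% / 26% | 0.657 | 0.615 | 0.658 | +0.1 | about 0% |
| 40% / 21% | 0.659 | 0.616 | 0.671 | +1.2 | 3% |
| 45% / 16% | 0.657 | 0.615 | 0.690 | +3.3 | 8% |
| 50% / 11% | 0.658 | 0.615 | 0.722 | +6.4 | 16% |

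The last column is [(1.96 + z_CMH)/(1.96 + z_Pearson)]² − 1, where z is the normal quantile of the power. For the bottom row: (2.549/2.367)² − 1 = 0.16.

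- With a 30:70 unit split, CMH power is 0.668 at 44%/25%, 0.685 at 51%/22% and 0.709 at 58%/19%, against 0.658 for Pearson. The gains are about 1, 2.7 and 5.1 points.
- At N = 1000 with equal units, CMH gives 0.961 (40%/21%) and 0.976 (50%/11%), against 0.955. The gain is at most about 2.1 points.
- Null rejection at N = 420 is 5.0% for Pearson and CMH, and 3.9% for Yates.

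**Dropping Yates alone.** From the table, Pearson minus Yates is 4.2 to 4.3 points at N = 420. At N = 1000 it is 0.955 − 0.948 = 0.7 points. No covariate is involved.

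**Logistic model with arm, unit, age and Charlson index** (30,000 trials per scenario, N = 420):
- Nothing prognostic: 0.657 against Pearson 0.661, −0.4 points.
- Unit odds ratio 2.5, with age and Charlson index each 1.25 per standard deviation: 0.680 against 0.662, +1.8 points.
- The same with 1.5 per standard deviation: 0.689 against 0.654, +3.5 points.

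A repeat simulation gave −0.3, +2.2 and +4.0. Adjusted null rejection was 4.8% to 5.0%, and the 95% interval for the standardised risk difference covered 94.7% to 95.1%. Expected events are 210·0.303 + 210·0.203 ≈ 106, ample for four model terms. With stronger assumed covariates (R² about 0.24), adjusted power reached about 77%, against 66% for Pearson.

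**Chance imbalance.** The between-arm difference in unit share has standard deviation √(0.25·2/210) = 4.9 points. At 40%/21%, a one-SD imbalance shifts the crude difference by 0.049·19 ≈ 0.9 points with no treatment effect. With the effect, the unit gap averages (19 + 0.67·19)/2 ≈ 15.9 points and the shift is about 0.8. Either is small against a standard error of 4.2 points.

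**The case against.** The plan contains no error on this point. An unadjusted primary comparison after simple patient-level randomisation is a legitimate choice, and some would call adjustment a preference. That stands, and it caps the weight of the point.

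The covariate gain is wholly assumed. At modest unit differences it is negligible, and the larger gains need rates as far apart as 45%/16% or 50%/11%. At 1000 patients, within the planned range, unit stratification adds little. If the 10% is a relative reduction, power at 420 is only about 10% with or without adjustment. All of this stands too.

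The one gain that needs no prognostic assumption comes from dropping Yates, which is not an adjustment issue. At 40%/21%, moving from the planned test to CMH gains 0.671 − 0.616 = 5.5 points, of which 4.3 are Yates. The two must be kept apart. The missing confidence interval is likewise a wider gap than adjustment.

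The small-loss figures come from simulations with complete covariates. They are not proven bounds, and missing Charlson values were not examined.

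Finally, the plan assigns no test to its primary endpoint. The main aim speaks of HAI incidence, while the Study design section speaks of the global incidence of sepsis. Using at least one HAI follows the main aim and the pilot count, but that conflict needs settling separately. None of this removes the asymmetry: the cost is a fraction of a point, and the possible gain is several.

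**Conclusion.** The concern holds as an improvement to consider, not as a fault that threatens validity. The planned comparison is valid, slightly conservative because of Yates, and uses none of the baseline information the trial will hold.

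At 420 patients in total, with 30.3% against 20.3%, stratifying by unit changes power by −0.2 to +6.4 points over the unit differences tried. A logistic model adding age and Charlson index loses about 0.4 points if nothing is prognostic and gains about 2 to 4 points under moderate assumptions, or about 11 under strong ones. At 1000 patients, stratifying by unit gains at most about 2 points. Removing Yates is worth about 4 points at 420 and 0.7 at 1000, whatever the covariates do.

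Where the trial falls in these ranges depends on unit differences and prognostic strengths that the documents do not give. The highest adjusted power found at 420 was about 77%, so adjustment does not close the gap to the stated 90%. That is a sample-size problem, separate from this one and larger.

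**What to change.** Name one primary analysis of at least one HAI per patient in the Data analysis section, in advance. There are two suitable forms:

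- a Cochran-Mantel-Haenszel test stratified by unit, without continuity correction, with a stratified risk difference and 95% confidence interval; or
- a logistic model with arm, unit, age and Charlson index, reported as a standardised (marginal) risk difference with 95% confidence interval, so that the result is not left as a conditional odds ratio.

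Keep the crude comparison as supportive. If the logistic model is chosen, state how missing Charlson values will be handled. Make unit an explicit item on the case report form. Randomising within unit is optional. First confirm that HAI, and not sepsis, is the primary endpoint.

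The cost is one or two sentences and a check of the form, with no extra patients.

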## **Aims of the study**

### *Main aim:*

Evaluation of the effect of daily bathing with 4% chlorhexidine gluconate (CHG)-containing soap on the incidence of HAI in 2 intensive care units.

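### The plan prespecifies significance tests but no effect estimate or confidence interval for the main outcome, and no rule for reading a non-significant result

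*Combined protocol and SAP*

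**What the plan says.** The main aim is "Evaluation of the effect of daily bathing with 4% chlorhexidine gluconate (CHG)-containing soap on the incidence of HAI in 2 intensive care units". The Sample Size section works from a pre-trial count ("Twenty patients out of 66 suffered from at least 1 HAI (incidence 30.3"%), an "alpha error tolerance (false-positive risk) equal to 0.05", "power equal to 0.9" and "a potential reduction of HAI incidence by 10"%. It does not say whether that 10% is absolute or relative. The Data collection section allows a total of 420 to 1000 patients, allocated 1:1.

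The Data analysis section is the whole analysis plan. It has a check of distributions, descriptive summaries (counts and percentages for categorical variables) and one sentence on comparing the arms: "Comparison between groups will be performed with two-tailed t-test, Mann-Whitney test or chi-square test with Yate's correction, depending on variable distribution". HAI is counted per patient as present or absent, so its planned comparison is the Yates-corrected chi-square. No section names a risk difference, risk ratio, odds ratio, rate ratio or confidence interval for any outcome, and none says how a non-significant result will be read.

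The Study design section describes the main comparison differently: "We will evaluate and compare the global incidence of sepsis in the two arms".

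**The concern.** An aim of evaluating an effect calls for an estimate of that effect and its uncertainty. A chi-square p-value gives neither, and it cannot be compared with the reduction the trial was sized to detect.

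This matters most when the test is not significant. Such a result can mean that the planned reduction is ruled out, or that the trial was too imprecise to tell. The Introduction says that existing studies disagree, so this distinction is much of what a new trial can add. Because the total may fall anywhere from 420 to 1000, precision is not fixed in advance either. With no prespecified measure, interval method or reading rule, all three can be chosen after the results are known.

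**Working it through.** **Inputs.** Control risk 20/66 = 30.3%, two-sided alpha 0.05, power 0.90 and dropout 5% to 8% (Sample Size); 1:1 allocation and a total of 420 to 1000 (Data collection); Yates chi-square (Data analysis). Assumptions: the 10% is absolute (30.3% to 20.3%) unless stated otherwise; 210 or 500 patients per arm are analysed, with no dropout; intervals are 95% Newcombe intervals for control minus CHG, so a positive value is a reduction.

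**1. The plan's own sample size.** Per arm,

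n = [1.96·√(2·0.253·0.747) + 1.2816·√(0.303·0.697 + 0.203·0.797)]² / 0.10² = 395.1, so 396.

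The total is 792 before dropout, 792/0.95 = 834 with 5% dropout and 792/0.92 = 861 with 8%. The stated 410–420 is not reproduced as a total. It is close to a per-arm figure (396/0.95 = 417), which favours the absolute reading; a relative 10% reduction would need about 9,380 patients in total. The gap between the per-arm and total figures is a separate matter. It is relevant here because it makes a non-significant result likely at the lower enrolment limit.

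**2. How often the problem arises.** Each probability is a full sum over both binomials,

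Σ Bin(x₁; n, p₁)·Bin(x₂; n, p₂)·1{condition}.

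| True risks (control, CHG) | Quantity | 210 per arm | 500 per arm |
|---|---|---|---|
| 30.3%, 20.3% | Yates test non-significant | 38% | 5% |
| 30.3%, 20.3% | Of those, interval includes 10 points | 93% | 51% |
| 30.3%, 30.3% | Interval lies below 10 points | 61% | 93% |
| 30.3%, 30.3% | Interval lies below 3.03 points (10% read as relative) | 10% | 18% |

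The 38% is 1 − 0.616, the exact power of the Yates test at 210 per arm.

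**3. Two hypothetical non-significant results at 210 per arm.** The Yates statistic is N(|ad − bc| − N/2)² / (n²·m·(N − m)), where N = 420, n = 210 and m is the total number of events.

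- 64 vs 63 events: |64·147 − 63·146| = 210, and 210 − 210 = 0, so p = 1.00. The difference is 0.5 points (−8.3 to 9.2). A 10-point reduction is excluded.
- 64 vs 52 events: |64·158 − 52·146| = 2520, and 2520 − 210 = 2310. The statistic is 420·2310² / (210²·116·304) = 1.44, so p = 0.23. The difference is 5.7 points. The Wilson limits are 24.6% to 37.0% (control) and 19.4% to 31.0% (CHG), so the lower limit is 0.0571 − √(0.0583² + 0.0626²) = −0.028 and the upper limit is 0.0571 + √(0.0653² + 0.0535²) = 0.142. A 10-point reduction is not excluded.

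The planned test calls both non-significant. The interval separates them.

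**4. Whether an interval can simply be added beside the Yates test.** At 210 per arm with a true 10-point effect, 4.2% of all trials have a Yates p above 0.05 while the Newcombe interval lies wholly above zero, in favour of CHG. That is 4.2/38.4 = 11% of the non-significant trials. The test and the interval therefore need to be matched.

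**The case against.** - *The information is not lost.* This stands. Counts and percentages are planned, the outcome is binary and allocation is by patient, so anyone can compute a risk difference and interval from the arm totals, as was done above. A reader might infer that the trial could never show whether the planned reduction was excluded; the documents do not support that. The gap is in what is prespecified and reported.
- *Nothing says that p > 0.05 means bathing does not work.* This also stands. A reader might infer such a rule from a plan that lists only tests, but the Data analysis section has no reading rule of any kind.
- *The 10-point target is an assumption.* It is. The sample size arithmetic favours it, but the text does not settle it. Under the relative reading even 1000 patients would rarely exclude the target. The omission is the same on either reading.
- *Much of the size comes from low power at 420 patients.* Correct. Reporting an interval does not lower the 38% miss rate, which falls to 5% at 1000 patients. The interval shows what the data can and cannot exclude at whatever size is reached.

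**Conclusion.** The point holds as one of prespecification and reporting. The plan sets out to evaluate an effect and sizes the trial for a reduction, but commits only to arm percentages and tests. It has no estimate, no interval and no rule for a non-significant result. The Yates test itself remains valid, and neither conduct nor data collection is affected, so this should be changed but does not undermine the trial.

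The size depends on enrolment and on how the 10% is read. On the absolute reading with a 30.3% control risk, a non-significant result at 420 patients is common even when the effect is real, and it seldom excludes that effect. At 1000 patients it is rare, and about half the time its interval still includes 10 points. If bathing has no effect, the interval would exclude 10 points in 61% of trials at 420 patients and 93% at 1000. On the relative reading these fall to 10% and 18%. Dropout would widen the intervals somewhat.

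**What to change.** In Data analysis:

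- Make the main result the risk difference, defined as control minus CHG (positive means a reduction), with a two-sided 95% confidence interval. Add the risk ratio with its interval.
- Replace the Yates test for this comparison with one that matches the interval, for example the uncorrected score chi-square with a Miettinen–Nurminen score interval.
- State the reading rule: when the result is non-significant, conclude that the planned reduction is excluded only if the upper confidence limit lies below it; otherwise call the result inconclusive.
- Give the same estimates and intervals for each secondary infection.

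In Sample Size, state whether the 10% is absolute or relative; the reading rule cannot be applied until this is settled. Reconcile the main outcome between Main aim (HAI) and Study design (sepsis), and attach the main estimate to whichever is kept.

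The cost is a few sentences of plan text and slightly more reporting. No new data are needed, and standard software gives these figures.

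### The main comparison uses none of the baseline risk factors the trial plans to collect; the crude test is valid, but precision may be lost to the extent that those factors predict HAI

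*Combined protocol and SAP*

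**What the plan says.** The Data analysis section is the whole analysis plan. Its only sentence on comparing the arms reads "Comparison between groups will be performed with two-tailed t-test, Mann-Whitney test or chi-square test", the last with Yates' correction and the choice left to how each variable is distributed. For a yes/no HAI outcome this means a chi-square test with continuity correction. No regression model, stratified test or covariate adjustment is mentioned in any section.

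Baseline risk factors are nevertheless to be recorded. The Study design section plans to collect, besides demographic data, "data about comorbidities, cause of admission and infections occurred during the hospital stay". The Data collection section puts sex, age and comorbidities on the case report form (CRF), the last "evaluated by Charlson comorbidity index". That section does not list cause of admission, and the CRF itself (attachment 1) is not part of the text available for review.

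Allocation is simple 1:1 randomisation by patient, without stratification or minimisation (Data collection). The planned size is 420 to 1000 patients (Sample Size and Data collection).

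**The concern.** Age, comorbidity and reason for admission are plausible predictors of infection in intensive care. If they do predict HAI, a crude comparison leaves explainable outcome variation in the error term, and adjustment would remove it using data the trial intends to hold anyway. Simple randomisation does not remove it by design. At 420 patients the arms will differ on any one baseline factor by more than 1.96 × 2/√420 = 0.19 standard deviations in about 5% of trials.

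Two things are at stake. One is precision for the main aim, where power at the lower planned size is already short. The other is prespecification: with no covariates named, any adjusted analysis added after a baseline imbalance is seen would be post hoc.

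**Working it through.** **Inputs from the Sample Size section.** The control risk is 20/66 = 0.303. The effect is "a potential reduction of HAI incidence by 10" per cent, read here as absolute, so 0.303 to 0.203; the section does not say absolute or relative. It also gives "alpha error tolerance (false-positive risk) equal to 0.05" and "beta error tolerance (false-negative risk) equal to 0.1, power equal to 0.9". A two-sided test is assumed.

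**Input not in the documents.** The predictive strength of the covariates is assumed and shown as a range of C-statistics.

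**Step 1: the plan's own figure.** With mean risk 0.253,

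n per arm = [1.960·√(2·0.253·0.747) + 1.282·√(0.303·0.697 + 0.203·0.797)]² / 0.10² = (1.2050 + 0.7827)² / 0.01 = 395.1, so 396.

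The total is 792 before dropout. The stated 410-420 does not reproduce as a total. It is close to a per-arm number: 396/0.95 = 417 and 396/0.92 = 431. That is a separate matter, but it sets the baseline for this one.

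**Step 2: crude power, no dropout, no continuity correction.** Power = Φ[(0.10·√n − 1.2050)/0.6107], with n per arm.
- 420 patients (n = 210): Φ(0.400) = 65.5%.
- 1000 patients (n = 500): Φ(1.688) = 95.4%.

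**Step 3: how much adjustment reduces the variance.** Trials were simulated at 0.303 versus 0.203 with 420 patients, 4000 per setting. Each had one normally distributed prognostic score plus 2 or 5 pure-noise covariates. The adjusted estimate is a logistic regression standardised to a marginal risk difference. The ratio is its variance divided by that of the crude difference.

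| Assumed C-statistic | Ratio, 2 noise covariates | Ratio, 5 noise covariates |
|---|---|---|
| 0.55 | 1.005 | 1.009 |
| 0.60 | 0.98 | 0.99 |
| 0.65 | 0.96 | 0.95 |
| 0.70 | 0.91 | 0.92 |
| 0.74 | 0.87 | 0.85 |

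A separate set of 3000 trials per scenario gave 0.94-0.96 at 0.65, 0.93 at 0.70 and 0.85-0.86 at 0.74. Type I error in its null runs was 4.3% to 5.5%.

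**Step 4: convert to patients and power.** A ratio v acts like a sample of N/v, so the gain is N/v − N patients. Power follows from Step 2 with n/v in place of n.

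| v | Patients gained at 420 | Power at 420 | Power at 1000 |
|---|---|---|---|
| 1.00 | 0 | 65.5% | 95.4% |
| 0.98 | 9 | 66.4% | 95.8% |
| 0.96 | 18 | 67.3% | 96.1% |
| 0.91 | 42 | 69.6% | 96.9% |
| 0.85 | 74 | 72.6% | 97.7% |

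At v = 1.009, the worst value simulated, the loss at 420 is about 4 patients, or 0.4 points of power.

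**Step 5: keep the continuity correction apart.** In a further simulation at 420 patients and a C-statistic of 0.70, power was 60.6% for the Yates-corrected chi-square, 64.4% for the uncorrected chi-square and 69.3% for the adjusted analysis. So about 4 of the 9 points come from dropping the correction and about 5 from adjustment. The figures in Step 4 count adjustment only.

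**Step 6: would adjustment rescue 420 patients?** Reaching 90% power would need v = 420/792 = 0.53, a 47% variance reduction. The largest reduction in the range is about 15%.

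**The case against.** The strongest reply is that nothing is wrong with the planned inference. Under simple randomisation the crude test is valid, and chance imbalance is already covered by its error rate. The plan never promises an adjusted analysis, so it does not contradict itself. All of that stands. A reader might infer from the absence of balancing that the crude estimate is biased or its type I error inflated; the documents do not support that.

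It can also be said that the gain is speculative. No section gives the covariates' predictive strength, and at C-statistics of 0.55 to 0.60 the gain is 0% to 2%. The simulated model is correctly specified and has no missing values, which is kinder than real data. Cause of admission probably overlaps with the admission unit (general or post-cardiosurgical), so the gain beyond any adjustment for unit could be smaller; it was not estimated. These points stand too, and are why the range must start at zero.

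The plan has physicians blinded to arm analyse the data, which limits steering an adjusted model towards a preferred result. This softens the prespecification worry but does not replace naming the covariates.

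None of this favours the crude test as the main analysis. The standardised risk difference targets the same marginal effect, and the cost when the covariates do not predict is negligible.

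**Conclusion.** The point holds as one of efficiency only. The plan would collect plausible predictors of HAI and use none of them in the main comparison. For assumed C-statistics of 0.55 to 0.74, using them would cut the variance of the risk difference by about 0% to 15%. That is worth about 0 to 75 patients or 0 to 7 points of power at 420, and at most about 2 points at 1000.

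These sizes rest on a 10-point absolute reduction, a two-sided 5% test, no dropout and an assumed predictive strength. A reader might take precision to be certainly lost, or adjustment to repair the sample size. Neither follows. The loss depends on a quantity the documents do not give, and at 420 patients even the favourable end reaches only about 73% against the stated 90%.

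**What to change.** In the Data analysis section, make the main analysis a logistic regression of HAI (yes/no) on arm, age (continuous), Charlson index (continuous) and cause of admission, in categories fixed before unblinding. First confirm that cause of admission is on the CRF, since the Data collection section does not list it. Then:

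- report the standardised (marginal) risk difference and risk ratio, each with a 95% CI;
- state a simple rule for missing covariates, for example single imputation of baseline values blind to arm and outcome;
- keep the crude chi-square as a sensitivity analysis.

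The cost is one paragraph of text and slightly more analysis work. It needs no extra patients and, if the CRF check succeeds, no new data. If the covariates turn out not to predict HAI, the loss of precision is negligible (under 1% of variance in the simulations).
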